3.2.3 Follow-up

Survival status will be collected by hospital research staff for all participants up to 180 days.

For patients who have been discharged, a tele-video clinic or out-patient follow-up visit will be arranged at 6 months after randomisation by a member of the research team from Imperial College London, where the FIM score will be documented, along with the other relevant data. If the patient is still in hospital, hospital research staff will aim to obtain their data by visiting them and if required, assisting them with the completion of this questionnaire.

4. ADVERSE EVENT MANAGEMENT

4.1 Definitions

Adverse Event (AE)	An Adverse Event is defined as any untoward medical occurrence in a participant administered a medicinal product and which does not necessarily have a causal relationship with the administration of the IMP.
Serious Adverse Event (SAE)	A Serious Adverse Event is an AE that fulfils one or more of the following criteria: 
 • Results in death • Is life-threatening • Requires hospitalisation or prolongation of an existing inpatient hospitalisation • Results in persistent or significant disability or incapacity • Is a congenital abnormality or birth defect • Requires medical intervention to prevent one of the above, or is otherwise considered medically significant by the investigator (e.g. participant safety is jeopardised).
Related SAE	An SAE where there is a potential for there to be a causal relationship to the intervention.
Related and Unexpected SAE	A related serious adverse event that is also unexpected i.e. the nature, frequency or severity of the event is not consistent with what is expected for the intervention of study.

4.2 Recording Adverse Events

This trial is comparing two interventions that are already in routine use in NHS clinical practice, and as such, only those Adverse Events that are assessed as being serious will be collected on a Serious Adverse Event CRF.

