----------	--------------------------	----

TRIAL SUMMARY

Trial Title	Randomised controlled trial of the clinical and cost-effectiveness of cervical spine immobilisation following blunt trauma (SIS trial)	
Internal ref. number (or short title)	SIS trial	
Trial Design	A multi-centre, open-label, pragmatic, pre-hospital, non-inferiority randomised controlled trial with health economic evaluation to determine the effectiveness of immobilisation regimes involving movement minimisation and triple immobilisation (current NHS practice) in patients with cervical spine (c-spine) injury recruited in a pre-hospital setting.	
Trial Participants	Patients (any age) in a pre-hospital setting with potential or suspected c-spine injury.	
Planned sample size	8,316 participants	
Treatment Duration	The interventions will be administered at initial pre-hospital clinical assessment and will remain in place for as long as is clinically required.	
Follow-up Duration	Participants will be followed-up for 180 days	
Planned Trial Period	01 November 2022 – September 2025 with an internal pilot phase 01 November 2022 – 30 April 2023	
	Objectives	Outcome Measures
Primary	To determine whether movement minimisation is deemed non-inferior compared to triple immobilisation in relation to functional outcome at hospital discharge.	Functional Independence Measure (Motor) score
Secondary	To determine the effects of immobilisation techniques on clinical, patient-centred and economic outcomes pre-hospital, in hospital and at 180 days post-randomisation.	Need for pre-hospital analgesia Neurological change (randomisation to hospital discharge) Mortality (30, 90 and 180 days) Length of stay in critical care and hospital Further intervention for c-spine injury Costs and resource utilisation Adverse events
Quality of Life	To determine the effects of immobilisation techniques on patient-centred outcomes pre-hospital, in hospital and at 180 days post-randomisation.	Quality of life measurements (EQ-5D-5L/EQ-5D-Y)

LIST OF ABBREVIATIONS/GLOSSARY

Abbreviation	Explanation
AE	Adverse Event
ASIA	American Spinal Injury Association Impairment Scale
CI	Chief Investigator
CONSORT	Consolidated Standards of Reporting Trials
CRF	Case Report Form
C-spine	Cervical spine
CTU	Clinical Trials Unit
DMC	Data Monitoring Committee
EQ-5D-5L	EuroQol five-domain health utility measure (five level)
EQ-5D-Y	EuroQol five-domain health utility measure (Youth)
FIM	Functional Independence Measurement
GCP	Good Clinical Practice

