1.3 Need for a trial

Spinal Immobilisation has been an essential standard of potential spinal injury care for 20 years³. However, gold standard “Triple Immobilisation” can be associated with neurological harm (for example if used in patients who unknowingly have ankylosing spondylitis)^{4,5}. The natural history following spinal cord injury (SCI) is that it often worsens as cord contusion progresses and this may mistakenly be attributed to lack of immobilisation. Hence the costs of not understanding SCI and immobilisation include not just the cost of collars (in UK ~ £500,000 year), but the cost of health complications and associated medico-legal costs, which can be considerable⁶. There is a significant body of opinion questioning the benefits of cervical immobilisation^{7,8}. Several ambulance services in Scandinavia and Australia have reduced the use of cervical collars, without an overt increase in complications. This is known as movement minimisation. Movement minimisation uses head blocks or rolled blankets to minimise movement in coronal plane, with the option to sit up (if desired and not contraindicated due to other reasons) on an ambulance stretcher. However, robust evidence is needed to know if movement minimisation is non-inferior than triple immobilisation before adopting

across the NHS given the substantial personal, healthcare and medico-legal consequences of SCI⁹. It is vital that a well-structured trial resolves this issue.

A survey of 614 health care professionals (373 Pre-Hospital Care, 154 Emergency Medicine, 34 Neurosurgery, 11 ITU, 11 Care of Elderly and 11 Anaesthetics) has demonstrated that 80% feel that current c-spine immobilisation guidelines are not appropriate. The majority (81.4%) were happy to randomise patients with potential spinal injury to either triple immobilisation or movement minimisation techniques with 64.4% thinking this should not be restricted to a specific conscious level. Respondents prioritised incidence of neurological deficit (58.6%) and a functional outcome measure (49.9%) as primary outcome measures. This proposal describes a definitive randomised trial to determine the clinical and cost effectiveness immobilisation regimes for spinal cord injury.

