4.3 Reporting Serious Adverse Events to the coordinating centre

The assessment and reporting of SAEs and related SAEs will follow the relevant Warwick CTU SOPs. Once a serious adverse event has been identified, information should be sent to the WCTU team at [contact], the WCTU QA team at [contact] and the Sponsor's Office at [contact] within 24 hours of the site becoming aware of the event. Reportable events should be recorded on the trial SAE form. The participant should continue to be followed-up until resolution of the event or a final outcome has been reached. Following reporting of a serious adverse event, any change of condition or other follow-up information should be reported by the same mechanism.

Events should be reported as a serious adverse event only if they:

- occur between randomisation and hospital discharge
- are serious (meet the criteria for Serious Adverse Events) AND are potentially related to trial participation, i.e. may have resulted from trial treatment;
- are not on the list of SAEs exempt from reporting (see section 4.3.1)

Examples of events that may be SAEs are;

- Use of one of the interventions causing a new injury that endangers the patient
- Unexpected cardiac arrest
- Sepsis related to use of collar
- Neuro-deficit

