4.3.1 SAEs exempt from reporting

Some events are anticipated as a result of the injury that has led to immobilisation of the spine, rather than the immobilisation itself. Many will be hospitalised with some requiring a stay in ICU/HDU. The following events will not need to be reported to WCTU because they are recorded in the CRF as an outcome or are anticipated as a result of the spinal injury rather than the intervention being studied:

- wound/skin breakdown
- pneumonia/chest infection
- evidence of intercranial hypertension
- other events directly attributable as a result of the participant's spinal injury

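### Section 4.2 calls both methods routine in the NHS, which the protocol contradicts elsewhere; separately, SAE reporting of a neurological deficit turns on a site attribution with no blinding stated

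*Protocol*

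**What the plan says.** On recording, section 4.2 gives as its reason that the trial compares "two interventions that are already in routine use in NHS clinical practice", and concludes that "only those Adverse Events that are assessed as being serious will be collected on a Serious Adverse Event CRF".

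On the standing of the two methods, the trial summary has "triple immobilisation (current NHS practice" and attaches no such label to movement minimisation. Section 1.3 says "robust evidence is needed to know if movement minimisation is non-inferior than triple immobilisation before adopting", and the sentence goes on to refer to adoption across the NHS. The same section places the experience with movement minimisation abroad: "Several ambulance services in Scandinavia and Australia have reduced the use of cervical collars, without an overt increase in complications". Section 2.9.1 ties only the control to the JRCALC guidelines.

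On SAE reporting, section 4.3 requires that events fall between randomisation and discharge, that they "are serious (meet the criteria for Serious Adverse Events) AND are potentially related to trial participation, i.e. may have resulted from trial treatment", and that they are not on the exempt list. Its examples of possible SAEs include "Neuro-deficit". The exempt list in section 4.3.1 ends with "other events directly attributable as a result of the participant", the phrase continuing with the spinal injury. Section 4.4.1 gives the causality judgement to a delegate of the principal investigator at the site.

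**The concern.** Two separate things look wrong.

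First, an ethics committee or DMC reading section 4.2 is told that both arms are established NHS care and that lighter recording follows from this. For the experimental arm the rest of the protocol says otherwise.

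Second, neurological worsening is the harm most feared when a collar is omitted, and the SAE route handles it ambiguously. The same deficit can be reportable at one site and exempt at another, depending on whether the assessor ascribes it to the treatment or to the injury. No blinding is stated for that judgement. Section 2.10.1 offers blinding only to outcome assessors, and only where possible. Section 4.4.3 has the DMC review SAEs by randomised arm, so an attribution that varies with knowledge of the arm feeds straight into that comparison.

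**Working it through.** The plan gives no figure on this point, so there is none to reproduce. The check sets the passages side by side.

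**1. The premise in 4.2.**

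| Place | Triple immobilisation | Movement minimisation |
|---|---|---|
| Section 4.2 | routine in the NHS | routine in the NHS |
| Trial summary | current NHS practice | no such label |
| Section 1.3 | described as the gold standard | use reported abroad; evidence needed before NHS-wide adoption |
| Section 2.9.1 | tied to JRCALC | not tied to JRCALC |

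Section 4.2 stands alone in the right-hand column.

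**2. The SAE route compared with the ASIA route.** Section 2.3 defines neurological deterioration as a change from ASIA grade E to any of A-D. Suppose that a serious deficit appears or worsens after the first in-hospital ASIA grade and before discharge, in a participant who survives to a discharge grade:

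| Change in ASIA grade | Site judgement | Reported as SAE? | Counted as deterioration? |
|---|---|---|---|
| E to A-D | possibly related to treatment | yes | yes |
| E to A-D | directly due to spinal injury | no (4.3.1) | yes |
| Worse within A-D | possibly related to treatment | yes | no |
| Worse within A-D | directly due to spinal injury | no (4.3.1) | no |

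The last row is missed by both the SAE count and the defined deterioration outcome, although the grades themselves are recorded. It concerns participants already impaired, in whom attribution to the injury comes most easily.

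**3. Effect on the comparison by arm.** Let W be the number of serious worsening events in an arm and p the probability that the site judges such an event potentially related. The expected SAE count in the arm is W × p, so the ratio of expected counts, movement minimisation (1) to triple immobilisation (0), is

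(W1 × p1) / (W0 × p0) = (W1/W0) × (p1/p0).

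With equal true risk and equal arm sizes, W1 = W0 and the ratio reduces to p1/p0. If assessors blame the missing collar, p1 exceeds p0 and the experimental arm looks worse than it is. If they lean on the injury exemption more in the experimental arm, p1 is below p0 and a real excess is diluted. Section 1.3 warns of the first error: natural progression of cord contusion may be wrongly put down to lack of immobilisation. The exemption in 4.3.1 leaves room for the second. The protocol gives no value for W or p in either arm.

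**4. What an exempt event bypasses.** It avoids the 24-hour report (4.3), review on receipt by the Chief Investigator or delegate, the 15-day REC route where related and unexpected, and the SAE table by arm (all 4.4.3). Neurological worsening is also not among the three safety outcomes in section 2.3.2.

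**The case against.** The case on the other side has four parts.

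- **Worsening is captured elsewhere.** Neurological change from randomisation to discharge is a secondary outcome (section 2.2.2). ASIA is collected near admission and at discharge in both arms with no attribution test (sections 3.1 and 3.2.2). The DMC sees interim outcomes after 624 patients and then every 6 months (section 7.10). This stands, and it means that neurological worsening is not left solely to the exemption, as a reader might infer from chapter 4 alone. The backstop is partial: the definition counts only E to A-D, a participant who dies before discharge (about 10% according to section 6.1) has no discharge grade, and six-monthly review does not replace event-level review.
- **The exemption does not rest on the routine-use claim.** A reader might infer that the false premise in 4.2 led to the exemption. The text does not support that. Section 4.2 uses the premise only to drop non-serious events, and 4.3.1 has its own reasons: the events are recorded as outcomes or are expected from the injury. Correcting 4.2 would leave 4.3 and 4.3.1 as they are, so these are two defects and not a chain.
- **Section 1.3 warns of the opposite error.** It describes natural worsening blamed on lack of immobilisation, which predicts over-reporting in the movement minimisation arm. This stands against any claim that the protocol itself predicts under-reporting there. It still shows that attribution is error-prone and tied to the arm.
- **Sections 4.3 and 4.3.1 can be read together.** A deficit that may be due to treatment is reported, and one directly due to the injury is not. Section 4.4.2 treats a possible relationship as related, so the threshold is low. That is fair, and the two are not a flat contradiction. But the reading works only if a site can separate the two causes, which section 1.3 suggests is difficult. The filter applies equally to both arms on paper; the difficulty is that the judgement behind it need not.

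**Conclusion.** The point holds in two limited parts. The routine-use statement in section 4.2 is contradicted for movement minimisation by the trial summary and sections 1.3 and 2.9.1, and must be reconciled with them. Separately, SAE reporting of a neurological deficit depends on a site attribution with no blinding stated, so SAE counts by arm and expedited review can be distorted in either direction.

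No size can be attached. A reader might try to derive one from the 1.8% prevalence of cord injury in major trauma in section 1.1. That figure counts people with an injury, in a narrower population than the trial's, and not worsening after randomisation, for which the protocol gives no rate. Nor does it give any basis for the share of events that sites would ascribe to the injury.

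The conclusion assumes that site assessors can know the arm, which is plausible in an open-label trial but is not stated. The primary FIM-motor analysis does not depend on SAE reporting. What is at stake is the reliability and timeliness of safety monitoring for the most feared harm, and the correction is worth making on that ground.

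**What to change.** 1. In section 4.2, correct the premise so that it agrees with the trial summary and sections 1.3 and 2.9.1, and give a reason for serious-only recording that does not depend on both methods being routine in the NHS.
2. In sections 4.3 and 4.3.1, state that any new or worsening neurological deficit from randomisation to discharge, including worsening within ASIA A-D, is reported in both arms regardless of local attribution, and that the last exemption does not apply to it.
3. Record the causality judgement separately on the form, so that it informs review without deciding whether the event is reported.
4. Tabulate these events by arm for the DMC, whatever their attribution.

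This changes reporting only. The cost is wording in three subsections and a modest number of extra SAE forms, partly overlapping the ASIA outcome already collected.

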4.3 Reporting Serious Adverse Events to the coordinating centre

The assessment and reporting of SAEs and related SAEs will follow the relevant Warwick CTU SOPs. Once a serious adverse event has been identified, information should be sent to the WCTU team at [contact], the WCTU QA team at [contact] and the Sponsor's Office at [contact] within 24 hours of the site becoming aware of the event. Reportable events should be recorded on the trial SAE form. The participant should continue to be followed-up until resolution of the event or a final outcome has been reached. Following reporting of a serious adverse event, any change of condition or other follow-up information should be reported by the same mechanism.

Events should be reported as a serious adverse event only if they:

- occur between randomisation and hospital discharge
- are serious (meet the criteria for Serious Adverse Events) AND are potentially related to trial participation, i.e. may have resulted from trial treatment;
- are not on the list of SAEs exempt from reporting (see section 4.3.1)

Examples of events that may be SAEs are;

- Use of one of the interventions causing a new injury that endangers the patient
- Unexpected cardiac arrest
- Sepsis related to use of collar
- Neuro-deficit

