4.4.1 Assessment of causality

Related SAEs are SAEs which are thought to have a potential for a causal relationship with the intervention. Causality should be assessed by a medical or clinical delegate of the PI at the investigator site. If an event is deemed to have a potential causal relationship, then this should be reported to WCTU via the mechanisms outlined in section 4.3. This should be followed by an expectedness assessment by an appropriately trained delegate of the Sponsor as per section 4.4.2 below.

The causality of SAEs (i.e. relationship to trial treatment) will be assessed by the investigator(s) on the SAE form using the following descriptions:

Relationship to trial medication	Description
Unrelated	There is no evidence of any causal relationship
Unlikely to be related	There is little evidence to suggest there is a causal relationship (e.g. the event did not occur within a reasonable time after administration of the trial intervention or device). There is another reasonable explanation for the event (e.g. the patient's clinical condition, other concomitant treatment).
Possible relationship	There is some evidence to suggest a causal relationship (e.g. because the event occurs within a reasonable time after administration of the trial intervention or device). However, the influence of other factors may have contributed to the event (e.g. the patient's clinical condition, other concomitant treatments).
Probable relationship	There is evidence to suggest a causal relationship and the influence of other factors is unlikely.
Definitely related	There is clear evidence to suggest a causal relationship and other possible contributing factors can be ruled out.

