4.4.3 Expedited reporting of events to REC

The trial manager will liaise with the investigator to compile all the necessary information. The trial coordinating centre is responsible for reporting any related and unexpected SAEs to the sponsor and REC within required timelines. All other recruiting sites in the trial will be informed of the event and any implications for the trial.

All SAE reports will be reviewed on receipt by the Chief Investigator or Co-Chief Investigator (or their delegate). SAEs that are deemed to be unexpected and related to the intervention will be notified to the REC and sponsor within 15 days of receipt in accordance with regulatory requirements. All such events will be reported to the Sponsor, Trial Steering Committee and Data Monitoring Committee at their next meetings. Reports of all SAEs by randomisation arm will also be reviewed by the DMC at their regular meetings, or more frequently if requested by the DMC Chair.

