4.5 Responsibilities

Principal Investigator (PI):

Checking for AEs when participants are reviewed or followed-up.

1. Using medical judgement in assigning seriousness and causality

2. Ensuring that all SAEs are recorded and reported to the Sponsor within 24 hours of becoming aware of the event and provide further follow-up information as soon as available. Ensuring that SAEs are chased with Sponsor if a record of receipt is not received within 2 working days of initial reporting.
3. Ensuring that AEs are recorded and reported to the Sponsor in line with the requirements of the protocol.

Chief Investigator (CI) / delegate or independent clinical reviewer:

1. Clinical oversight of the safety of patients participating in the trial, including an ongoing review of the risk / benefit.
2. Immediate review of all SAEs
3. Review of specific SAEs in accordance with the trial risk assessment and protocol as detailed in the Trial Monitoring Plan.
4. Production and submission of annual reports to the relevant REC.

Sponsor or delegate (WCTU):

1. Central data collection and verification of AEs, and SAEs, according to the trial protocol.
2. Expectedness assessment of related SAEs
3. Reporting safety information to the CI, delegate or independent clinical reviewer for the ongoing assessment of the risk / benefit according to the Trial Monitoring Plan.
4. Reporting safety information to the independent oversight committees identified for the trial (Data Monitoring Committee (DMC) and / or Trial Steering Committee (TSC)) according to the Trial Monitoring Plan.
5. Expedited reporting of related and unexpected SAEs to the REC within required timelines.
6. Notifying Investigators of related and unexpected SAEs that occur within the trial.

Trial Steering Committee (TSC):

In accordance with the Terms of Reference for the TSC, periodically reviewing safety data and liaising with the DMC regarding safety issues.

Data Monitoring Committee (DMC):

In accordance with the Terms of Reference for the DMC, periodically reviewing unblinded overall safety data to determine patterns and trends of events, or to identify safety issues, which would not be apparent on an individual case basis.

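### Section 4.3 makes the DMC's by-arm SAE table depend on unblinded site attribution, while 4.4.3 and 4.5 speak of all SAEs

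*Protocol*

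**What the plan says.** Section 4.3 opens without a relatedness condition: "Once a serious adverse event has been identified, information should be sent to the WCTU team", within 24 hours of the site becoming aware. It then sets an exclusive list of conditions, introduced by "Events should be reported as a serious adverse event only if they". Besides timing and absence from the exempt list, the condition is that events "are serious (meet the criteria for Serious Adverse Events) AND are potentially related to trial participation, i.e. may have resulted from trial treatment". Section 4.3.1 exempts events that are already CRF outcomes and, as a last item, other events that the site attributes directly to the spinal injury.

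Two later sections describe an unfiltered flow. Section 4.4.3: "Reports of all SAEs by randomisation arm will also be reviewed by the DMC at their regular meetings". Section 4.5 makes the PI responsible for "Ensuring that all SAEs are recorded and reported to the Sponsor within 24 hours of becoming aware of the event".

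Among its four examples of possible SAEs, section 4.3 lists "Sepsis related to use of collar". The collar is part of the control regimen (section 2.9.1).

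**The concern.** Relatedness to trial treatment is a different question in each arm, because the treatments differ and the person answering knows which was used. The trial is open-label. The blinding in section 2.10.1 applies where possible to outcome assessors and does not mention those who judge causality. If an SAE form is sent only after that judgement, the by-arm count mixes how often events happen with how readily they are blamed on the device. The table could show a difference where none exists or hide a real one.

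Section 4.5 asks the DMC to look for patterns that individual cases would not reveal. An event that no site thinks related, but that is more frequent in one arm, is such a pattern, and the 4.3 condition would remove it from the SAE table before the DMC looked.

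**Working it through.** **1. The reporting passages side by side**

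| Protocol section | Relatedness needed before an SAE is sent? |
|---|---|
| 4.3, opening paragraph | No |
| 4.3, list of conditions | Yes |
| 4.3.1, last exemption | Yes, in reverse: attribution to the injury removes the event |
| 4.4.1, opening | Yes: a site delegate of the PI assesses causality, and a potential relationship leads to reporting |
| 4.4.1, grading scale | Unclear: the form has an Unrelated grade ("There is no evidence of any causal relationship") that would be nearly empty under the 4.3 list |
| 4.4.3, DMC review | No |
| 4.5, PI duties | No |

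Section 4.2 ("only those Adverse Events that are assessed as being serious will be collected on a Serious Adverse Event CRF") states seriousness alone. It can be read as merely excluding non-serious events, so it adds little.

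Take a non-fatal cardiac arrest that the site thinks unrelated. Under 4.5 it is sent; under the 4.3 list it is not. This inconsistency between sites does not by itself bias the comparison, because randomisation is individual and 1:1. It makes the event count uninterpretable. Bias needs attribution to differ by arm.

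**2. Does the protocol give reason to expect attribution to differ?**

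It contains two cues, pointing in opposite directions.
- The sepsis example names the control device.
- Section 1.3 warns that cord injury often worsens naturally and that this may be wrongly blamed on lack of immobilisation. Neuro-deficit is a listed example SAE. The same deterioration could be read as the course of the injury in the collar arm (exempt under 4.3.1) and as a treatment effect in the movement-minimisation arm (reported).

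**3. How attribution enters the table**

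Let p1 and p0 be the true SAE risks (movement minimisation, collar), and a1 and a0 the probabilities that an SAE passes the site's judgement.

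Reported ratio = (p1 × a1) / (p0 × a0) = (p1/p0) × (a1/a0).

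The only input from the protocol is 4158 per arm (section 6.1), which is not in dispute. All values of p and a below are assumptions.

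Equal true risk of 2%, so 4158 × 0.02 = 83.2 events per arm:

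| a1 v a0 | Reported events | Reported ratio |
|---|---|---|
| 0.50 v 0.50 | 41.6 v 41.6 | 1.00 |
| 0.45 v 0.55 | 37.4 v 45.7 | 0.82 |
| 0.40 v 0.60 | 33.3 v 49.9 | 0.67 |
| 0.30 v 0.60 | 24.9 v 49.9 | 0.50 |
| 0.60 v 0.40 | 49.9 v 33.3 | 1.50 |

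The true risk cancels from the ratio. At 1% or 5% the ratios are the same and only the counts change (at 0.40 v 0.60: 16.6 v 24.9, or 83.2 v 124.7).

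Masking: a true 3% v 2% gives 124.7 v 83.2 events, ratio 1.5. With 0.40 v 0.60 attribution the table shows 49.9 v 49.9, ratio 1.0. With equal attribution of 0.50 it shows 62.4 v 41.6, and the ratio of 1.5 is preserved.

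**4. What bypasses the filter**

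- Pressure sores, aspiration pneumonia and intracranial hypertension are safety outcomes (2.3.2), and death is a CRF outcome (4.6).
- Section 3.2.2 collects infection, other injuries from randomisation to discharge, mortality, adverse events and ASIA grade, with no attribution condition.
- Of the four example SAEs, new injury and sepsis therefore have close counterparts.
- Neuro-deficit is partly covered: ASIA is recorded near admission and discharge, but section 2.3 defines deterioration only as a move from E to A–D.
- Cardiac arrest is covered only when fatal.

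**The case against.** The strongest reply is that most important harms never pass through the filter, as step 4 shows, and that the DMC also receives interim outcomes (section 7.10). This stands, and it confines the point to the by-arm SAE table. A reader might infer that the trial's whole or main harm comparison is distorted. The documents do not support that.

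Second, all SAEs in 4.4.3 and 4.5 may simply mean all reportable SAEs, the term used in section 4.4, and an Unlikely grade can follow a low initial threshold. That reading is possible, but neither section says so, and the opening of 4.3 sends any identified SAE. It also leaves a table described as covering all SAEs that contains only those a site thought potentially related.

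Third, the threshold is low, which limits the room for differential attribution, and nothing shows that attribution differs by arm. This stands: bias is a risk of the rule, not a demonstrated fact.

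Fourth, a reader might infer that the sepsis example makes one of four event types reportable only in the collar arm. The list gives examples and is neither exhaustive nor weighted by frequency. Crossovers are foreseen (2.12), and later collar use is recorded as an outcome (2.3.1). The example is a cue to attribution and does not measure lost events.

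Fifth, recording every SAE whatever its cause could be heavy among 8316 trauma patients, since hospitalisation is itself a seriousness criterion (4.1). Restricting SAE forms is a deliberate choice. It is defensible for expedited reports, but does not justify using the same forms as the basis of a by-arm comparison.

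**Conclusion.** The point holds in a limited form. The conditions in section 4.3 and the exemption in 4.3.1 filter SAEs by unblinded site attribution, while the opening of 4.3, section 4.4.3 and section 4.5 state no such filter. Compliant sites can send different events, and under the 4.3 rule the DMC's by-arm SAE table reflects attribution as well as occurrence.

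The size cannot be derived, because the protocol gives neither an SAE rate nor attribution probabilities. The product rule in step 3 is exact for expected counts, but the values put into it are assumptions. The protocol plans no significance test on SAE counts, so no error rate is claimed. The change is worth making because it is cheap and the DMC can recommend stopping; the efficacy analysis is not affected.

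**What to change.** 1. Reconcile the opening and the conditions of 4.3 with 4.4.3 and 4.5, so that one rule says which SAEs are sent. Keep relatedness and expectedness as the trigger for expedited reporting.
2. In the examples in 4.3, replace "Sepsis related to use of collar" with the arm-neutral Sepsis.
3. State that the DMC's by-arm harm tables use event types recorded for every participant in both arms regardless of attribution. Use the items already in section 3.2.2 (infection, other injuries, ASIA, mortality, listed adverse events), and add yes/no items to the existing discharge CRF for those not captured, such as non-fatal cardiac arrest and new neuro-deficit.
4. If the 4.3 restriction is kept, label the SAE-form table as SAEs judged potentially related and treat it as secondary. The injury-attribution exemption in 4.3.1 would still shape that table, which is a further reason not to rely on it.

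Cost: protocol wording and a few more tick-boxes on a form that staff already complete from the medical records. No extra participants, visits or assessors are needed.
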